- v. [name]; (University of Florida, Critical Care Medicine)
- vi. [name]; (JH-ACH, Institute for Clinical and Translational Research)
- vii. [name]; (JH-ACH, Critical Care Medicine)

2. Abstract

Critical asthma is disease of immune dysregulation that is acutely treated with inhaled beta-agonists and systemic corticosteroids. Steroid agents are chosen at the discretion of clinical providers based upon a child's capacity to tolerate enteral medications and the specific clinical setting (outpatient vs. general inpatient vs. critical inpatient). Intravenous methylprednisolone (MP) is unanimously used in the critical care (PICU) literature and populations but little data exists comparing MP to other potent intravenous corticosteroids such as dexamethasone (DM). Both drugs have been FDA approved for the acute treatment of inflammatory disorders including asthma, but no superiority trials have been conducted in the inpatient setting for this specific population.

Our research group has conducted a retrospective study over a 2-year period to assess if differences in clinical outcomes or adverse events exist in cohorts defined by DM exposure in the ER. Our data revealed none, but most children were switched to MP during their PICU stay making data analyses severely confounded by exposure to the defining characteristics of the comparative cohort. As both agents are FDA approved and in an effort to appropriate power sample size calculations for a prospective non-blinded clinical trial of DM vs MP in status asthmaticus, we seek to first prospectively study individuals enrolled into an interventional arm (DM) during their PICU asthma treatment and compare outcomes to PICU asthmatics concurrently admitted to the PICU enrolled into a parallel group, standard care arm (MP). This research will provide much needed epidemiologic and basic comparative data required to power and conduct a definitive, trials of DM vs. MP assessing other clinical efficacy endpoints

3. Study Endpoints:

Primary endpoints include (1) length of stay, (2) continuous albuterol duration, (3) a composite outcome including frequency of critical asthma adjunctive pharmacologic and respiratory-based interventions, and (4) corticosteroid-related adverse events

4. Background

As the pathophysiology of an critical asthma is dysregulated inflammatory pathways, standard treatment includes the prompt initiation of intravenous systemic corticosteroids. Glucocorticoids are the mainstay of therapy for children treated for critical asthma (Taylor, 1993). Furthermore, corticosteroids

improve the efficacy of beta-2 agonists, such as albuterol (Svedmyr, 1990), a nebulized medication used for bronchodilation in acute asthma exacerbations. There remains an ongoing dialogue among the expert medical community regarding the superiority of specific IV corticosteroid, dosing, route and delivery. This debate continues secondary to a lack of definitive comparative data in the literature. While the benefits of receiving systemic corticosteroids has been demonstrated in multiple studies (Scarfone, 1993; Ho, 1994; Connell, 1994; Storr, 1987; Younger 1987; Gleeson, 1990; Kattan, 1980), to date, no superiority trials have been conducted comparing IV systemic corticosteroids in the PICU setting.

While many systemic corticosteroids are FDA approved for the treatment of asthma exacerbation including prednisone, prednisolone, MP and DM, standard care in management of critical asthma is IV MP 1mg/kg/dose (max 60mg) every 6 hours for a 5-day course. Recent data from emergency room literature would suggest there is equipoise in use of dexamethasone as an alternative for methylprednisolone due to its increased glucocorticoid (anti-inflammatory) potency and long elimination half-life (Keeney, 2014; Paniagua, 2017). Steroids are chosen at the discretion of clinical providers based upon a child's capacity to tolerate enteral medications and clinical setting (outpatient vs. general inpatient vs. critical inpatient).

Our research group has conducted a retrospective study over a 2-year period to assess if differences in clinical efficacy endpoints or safety endpoints exist in cohorts defined by DM exposure in the ER. Our data revealed no differences, but many children were switched to MP during their PICU stay making data analyses severely confounded by exposure to the defining characteristics of the comparative cohort. We seek to prospectively consent individuals to receive DM (intervention arm) during their PICU stay and compare outcomes to a standard care arm (MP). The JH-ACH admits approximately 150 asthmatics per year in the PICU and we aim to enroll 90 subjects (30 intervention and 60 standard care) to detect a 1-day change in length of stay with a power of 0.8 and alpha set at 0.05. Primary outcomes include (1) length of stay, (2) continuous nebulized albuterol duration, (3) a composite outcome including rate of critical asthma adjunctive pharmacologic and respiratory interventions, and (4) rates for corticosteroid-related adverse events. We plan to use the findings of our study to inform the methodology of upcoming superiority trials to better understand how choice of corticosteroid may impact clinical, molecular, physiology efficacy endpoints.

5. Study Procedures

- a. *Study design:* After IRB approval, we will conduct a prospective, parallel-arm, non-randomized, open label, single-center, cohort study in children 5 to 17 years of age admitted to the JH-ACH PICU with critical asthma. Children consented to the interventional arm will receive intravenous (IV) DM 0.25 mg/kg/dose (max dose 15 mg per dose) every 6 hours for up to 2 days and those enrolled into standard care arm will receive IV MP 1 mg/kg/dose (max dose 60mg per dose) every 6 hours for up to 5 days.
- b. *Study duration:* Up until 30-days after hospital discharge following study enrollment.
- c. *Blinding:* None.
- d. *Justification of why participants will not receive routine care or will have current therapy stopped.* DM has an FDA approved indication for asthma exacerbation management. The use of DM has been adopted in the emergency room and inpatient acute care setting as standard care.
- e. *Definition of treatment failure or participant removal criteria.:* As the half-life for DM is such that 2 days of dosing is the equivalent of 5 days of steroid exposure, at the completion of day 4, if a child is still severely ill (at the discretion of the clinical provider in consultation with pediatric Pulmonology as part of standard care) was defined as treatment failure. Standard care would dictate further steroid administration at this time with either IV or PO corticosteroids beyond 5 days with planned taper in the inpatient/outpatient setting. If treatment failure occurs and IV steroids are elected to be continued beyond the prespecified duration, the clinicians could choose the corticosteroid type at their discretion.

f. *Description of what happens to participants receiving therapy when study ends or if a participant's participation in the study ends prematurely:* After children receive up to 2 days of DM, no further corticosteroids are indicated as the elimination half-life is such that it is an equivalent of 5 days of treatment with MP. Standard care for children admitted to the PICU for critical asthma includes the route modification from IV to enteral largely dependent on respiratory and mental status improvements. At that time, a child may be transitioned to enteral prednisone or prednisolone during standard care management (MP). If a child enrolled into the intervention arm (DM) receives < 2 days of IV DM but are ready to initiate enteral medications, then they will be switch to enteral DM 0.5mg/kg/dose daily for a total duration of exposure not to exceed 2-days during protocolized treatment.

g. *Inclusion/Exclusion Criteria:* Inclusion criteria are children 5 to 17 years of age with primary admission diagnoses of critical asthma (including both acute asthma exacerbation or status asthmaticus in the PICU setting). Exclusion criteria are children with existing tracheostomy, cystic fibrosis, malignancy, transplantation status, and pulmonary hypertension.

6. Drugs/ Substances/ Devices

ARM Name	Intervention Arm
Intervention Type	Dexamethasone (Intervention)
Dose Route	Intravenous
Dose Units	mg/kg
Dose Strength	0.25/dose (Max 15mg)
Dose Frequency	Every 6 hours
Sourcing	Clinical pharmacy
Packaging/Labeling	Per clinical standard

ARM Name	Intervention Arm
Intervention Type	Dexamethasone (Intervention)
Dose Route	Enteral
Dose Units	mg/kg
Dose Strength	0.5/dose (Max 16mg)
Dose Frequency	Daily
Sourcing	Clinical pharmacy
Packaging/Labeling	Per clinical standard

ARM Name	Standard Care Arm
Intervention Type	Methylprednisolone
Dose Route	Intravenous
Dose Units	mg/kg
Dose Strength	1/dose (Max 60mg)
Dose Frequency	Every 6 hours
Sourcing	Clinical pharmacy
Packaging/Labeling	Per clinical standard

ARM Name	Standard Care Arm
Intervention Type	Prednisone / Prednisolone
Dose Route	Enteral
Dose Units	mg/kg
Dose Strength	1/dose
Dose Frequency	Every 12 hours
Sourcing	Clinical pharmacy
Packaging/Labeling	Per clinical standard

- a. *Justification and safety information if FDA approved drugs will be administered for non-FDA approved indications or if doses or routes of administration or participant populations are changed:* Not applicable.
- b. *Justification and safety information if non-FDA approved drugs without an IND will be administered.:* Not applicable

7. Study Statistics

- a. *Primary outcome variables:* Primary outcomes include (1) length of stay, (2) continuous nebulized albuterol duration, (3) a composite outcome including rate of critical asthma adjunctive pharmacologic and respiratory interventions (i.e., magnesium, methylxanthines, terbutaline, ketamine, inhaled anesthetics, invasive mechanical ventilation, non-invasive ventilation, extracorporeal life support, and heliox), and (4) rates for corticosteroid-related adverse events (corticosteroids (i.e., clinically relevant gastrointestinal bleeding, gastritis, necrotizing enterocolitis, hypertension, hyperglycemia, altered mentation [hallucinations and delirium], and adrenal suppression)
- b. *Other study data to be collected:* anthropometrics, demographics, Pediatric Risk of Mortality-3 score Probability of Mortality, Pediatric Asthma Severity Score, National Heart Lung and Blood asthma classification, Pediatric Index of Mortality-3 score Risk of Mortality, comorbidities, and unplanned same-cause hospital readmission within 30 days
- c. *Statistical plan:* Descriptive statistics such as proportions/frequencies, means \pm standard deviation, and medians [interquartile range]. Comparative statistics will include Wilcoxon rank sum, Fisher's exact, and student's *t* tests where appropriate. Type I error will be set at 0.05. All data will be analyzed using Stata v15.1 (Statacorp©, College station, TX).

8. Risks

- a. *Medical risks, listing all procedures, their major and minor risks and expected frequency:*
 - i. There always exists a potential risk for data leak, loss of privacy and breach of confidentiality. All measures (described below) will be taken to minimize these risks.
- b. *Steps taken to minimize the risks:*
 - i. Patient data will be stored for research purposes as a HIPAA defined limited data set in a secure, password protected electronic database and analyzed with Stata v15.1. Each patient will be assigned a unique Participant ID number in the system. Access to the system will be restricted to research team members listed above. Data extractions as well as modifications or edits to data will be logged.

- ii. Serious adverse events will be followed throughout study, officially reported within 24-hours, and adjudicated within the co-investigator and steering committee. In the event that > 5% of children have a serious adverse event during enrollment, trial enrollment will be halted to prevent potential harm.
- c. *Plan for reporting unanticipated problems or study deviations:*
 - i. The principal investigator will meet on a monthly basis with study members either face-to-face or via telecommunications to discuss study management, education / re-education of team members and mentorship. This will include any discussion related to unanticipated problems or study deviations. This will not exclude team members from meeting with the principal investigator on other occasions to discuss matters as it relates to this study protocol. These meetings will be confidential and take place in a secure meeting room in the Johns Hopkins All Children's Hospital Pediatric Critical Care Medicine office in the [name]. Any deviations from the study protocol will be logged and immediately reported to the local JH-ACH IRB for review.
 - d. *Legal risks such as the risks that would be associated with breach of confidentiality:* see above.
 - e. *Financial risks to the participants:* none

9. Benefits

- a. This research will provide the needed epidemiologic and basic comparative data required to power and conduct a definitive, head-to-head trial of DM vs. MP. As a result of these data, definitive study with a randomized, RCT could be conducted to confirm superiority or non-inferiority of DM vs MP as well as assessment of other relevant endpoints.
- b. We expect that given the shorter treatment duration and potent glucocorticoid activity, DM will offer potential advantages related to patient compliance.

10. Payment and Remuneration: None

11. Costs: None

12. Discontinuation of Study Intervention and Participant Withdrawal:

- a. If a patient has a serious or non-serious adverse event thought to be associated with DM, then the IRB, subject, and family will be notified of any adverse events immediately.
- b. A participant may voluntarily withdraw from the study at any time at his/her own request (or consenting family member's request).

13. Regulatory and Ethical Considerations:

- a. The investigator will be responsible for the following:
 - i. Providing written summaries of the status of the study to the IRB/IEC annually or more frequently in accordance with the requirements, policies, and procedures established by the IRB/IEC
 - ii. Notifying the IRB/IEC of SAEs or other significant safety findings as required by IRB/IEC procedures
 - iii. Providing oversight of the conduct of the study at the site and adherence to requirements of 21 CFR, ICH guidelines, the IRB/IEC, European regulation 536/2014 for clinical studies (if applicable), and all other applicable local regulations

14. Informed Consent Process:

- a. The investigator or his/her authorized designee will explain the nature of the study to the participant or his/her legally authorized representative and answer all questions regarding the study.
- b. Participants must be informed that their participation is voluntary. Participants or their legally authorized representative will be required to sign a statement of informed consent that meets the requirements of 21 CFR 50, local regulations, ICH guidelines, Health Insurance Portability and Accountability Act (HIPAA) requirements, where applicable, and the IRB/IEC or study center.
- c. The medical record must include a statement that written informed consent was obtained before the participant was enrolled in the study and the date the written consent was obtained. The authorized person obtaining the informed consent must also sign the informed consent form (ICF).
- d. Participants must be re-consented to the most current version of the ICF(s) during their participation in the study.
- e. A copy of the ICF(s) must be provided to the participant or the participant's legally authorized representative.

15. Protocol Deviations

- a. A protocol deviation is any departure from the defined procedures and treatment plans as outlined in the protocol version submitted and previously approved by the IRB. Protocol deviations have the potential to place participants at risk and can also undermine the scientific integrity of the study thus jeopardizing the justification for the research.
- b. The JHM IRB requires the prompt reporting of protocol deviations which are:
 - i. Emergency deviations (when immediate deviations are required to protect the life or physical well-being of a participant)
 - ii. Major (representing a major change in the approved protocol), non-emergent deviation occurring without prior IRB approval
- c. Minor or administration deviations, which do not affect the scientific soundness of the research plan or the rights, safety, or welfare of human participants, are reported to the JHM IRB at the time of continuing review.

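### Outcome (4) lists adrenal suppression with no planned test, and hypertension and hyperglycemia with no common criterion or observation window, so its rates partly reflect what is tested and labelled

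*Combined protocol and SAP*

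**What the plan says.** Section 7a gives as its fourth primary outcome "4) rates for corticosteroid-related adverse events". The components are "clinically relevant gastrointestinal bleeding, gastritis, necrotizing enterocolitis", followed by "hypertension, hyperglycemia, altered mentation [hallucinations and delirium], and adrenal suppression". The only qualifier is the one on gastrointestinal bleeding, and it is not defined.

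Section 7b lists the other data to be collected: severity scores, demographics and similar items, ending with "comorbidities, and unplanned same-cause hospital readmission within 30 days". It has no cortisol, glucose or blood-pressure item. Section 5b sets the study duration as "Up until 30-days after hospital discharge following study enrollment", but no section describes a visit or test in that period. Section 8a asks for the risks of all procedures and answers only with data privacy, which fits a plan with no added blood test.

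Section 5c states that there is no blinding. Section 8b provides that "Serious adverse events will be followed throughout study, officially reported within 24-hours, and adjudicated within the co-investigator and steering committee". That covers serious events only, and it is done within the study team.

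**The concern.** A recorded adverse-event rate is the true rate multiplied by the share of cases detected. Nothing in the plan makes detection equal in the two arms, and for adrenal suppression nothing plans detection at all.

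Adrenal suppression as listed is a biochemical state. Without a test, only children who become clinically recognisable can be counted. The Background supports dexamethasone (DM) by "its increased glucocorticoid (anti-inflammatory) potency and long elimination half-life", so a reader will look at this line of the results with particular interest. A zero there could be read as a finding when the state was not measured.

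Hypertension and hyperglycemia are recorded in more ordinary ways, but the plan does not say what value counts, how many readings are needed or over which hours. Treating clinicians who know the arm decide when to measure and when to write the diagnosis. A difference between DM and methylprednisolone (MP) could then arise with no true difference, and a true difference could be hidden.

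**Working it through.** **The plan's own figure.** The protocol gives no expected rate, power or precision for outcome (4), so there is nothing to reproduce. Its only design figure is the sample size for a 1-day change in length of stay (section 4). The arm sizes used below, 30 DM and 60 MP, come from there. The test, Fisher's exact at 0.05, comes from section 7c.

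**Adrenal suppression: what a zero would show**

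1. If all 30 DM children were tested with a perfect test and none were positive, the exact two-sided 95% upper limit would be 1 − 0.025^(1/30) = 11.6%. For 0 of 60 MP children it would be 1 − 0.025^(1/60) = 6.0%.
2. If only a share *s* of true cases is detected, the chance of recording 0/30 at true rate *p* is (1 − *p·s*)^30. Take *p* = 20%, an assumption:
   - *s* = 100%: 0.80^30 = 0.1%
   - *s* = 25%: 0.95^30 = 21%
   - *s* = 10%: 0.98^30 = 55%
   - *s* = 0: 100%
3. The plan gives no basis for *s*, so the 11.6% limit cannot be claimed, and no other limit can replace it.

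**Hypertension and hyperglycemia: effect of unequal detection**

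Assumed inputs, none of them from the documents: a true risk *r*, equal in both arms, from 10% to 50%, and detection shares d(DM) and d(MP). The observed rates are *r*·d(DM) and *r*·d(MP). For example, at *r* = 50% with detection of 60% DM and 90% MP, they are 30% and 45%. The false-positive rate is the sum, over all tables (*a* of 30, *b* of 60) with two-sided Fisher p < 0.05, of Bin(*a*; 30, *r*·d(DM)) × Bin(*b*; 60, *r*·d(MP)). This was enumerated exactly.

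| True risk, both arms | DM 60%, MP 90% | DM 90%, MP 60% | DM 80%, MP 90% | DM 90%, MP 80% | Both 90% |
|---|---|---|---|---|---|
| 10% | 3.3% | 7.0% | 2.8% | 3.7% | 3.1% |
| 20% | 6.9% | 9.9% | 3.6% | 4.3% | 3.5% |
| 30% | 12.6% | 14.0% | 4.6% | 4.8% | 3.8% |
| 40% | 16.8% | 18.9% | 4.8% | 5.3% | 3.8% |
| 50% | 24.2% | 25.4% | 6.2% | 6.4% | 4.3% |

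Equal detection at other levels (60%, 80% or 100% in both arms) stays between 2.7% and 4.4%. The inflation is therefore material only when the component is common and the detection gap is wide.

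**Direction.** Three passages bear on it, and they do not agree. Section 5a allows IV MP for up to 5 days and DM for up to 2, which could mean more monitoring of MP children. Section 5f lets MP children move to enteral steroid as they improve, so 5 days is a ceiling. Section 12a's notification rule names only events thought to be associated with DM, which could raise recording in the DM arm.

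**The case against.** The strongest reply is that this is a preparatory study sized on length of stay, that cut-offs are often kept in a data dictionary, and that a large false-positive rate needs assumptions the documents do not supply. Much of this stands. With detection of 80% versus 90%, or with a true risk near 10%, the error rate stays at or near the nominal level. A figure of about 24% taken alone would overstate the problem. Missing cut-offs by themselves would be a matter of detail, although no data dictionary is cited. The reply does not reach the adrenal item, which is named as part of a primary outcome with no planned means of measuring it.

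A reader might also infer four stronger things that the documents do not support:

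- **That the adrenal count will be near zero whatever the truth.** Follow-up runs to 30 days after discharge, and symptomatic insufficiency can be recognised clinically.
- **That MP children will be tested more, which would favour DM.** The passages on direction point both ways. It is also not established that suppression would differ by arm, since sections 5e and 5f treat 2 days of DM as equivalent to 5 days of MP.
- **That the adrenal item contaminates a single pooled rate.** Section 7a uses the word composite for outcome (3) and plural rates for outcome (4), while the Study Summary refers to a single rate. Whether pooling is planned is unclear.
- **That a zero would enter a later trial's safety case.** The protocol says only that the data will inform the methods and power of later trials.

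**Conclusion.** The point holds in a limited form. As written, outcome (4) cannot support a conclusion about adrenal suppression. A zero would be informative about clinically recognised insufficiency and would set no upper limit on biochemical suppression. This follows from the text and needs no calculation.

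For hypertension and hyperglycemia, the comparison is open to differences in testing and labelling, of unknown direction. Under the assumed inputs, the false-positive rate runs from about 3% to 25% with 60% versus 90% detection, and from about 3% to 6% with 80% versus 90%, against about 3% to 4% with equal detection. The true risks and detection shares are illustrative. The result shows that the comparison is vulnerable, and does not show that it will be biased by any given amount. The change is worth making because a primary outcome is affected and the repair is cheap.

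**What to change.** In section 7a:

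1. Replace adrenal suppression with *clinically diagnosed adrenal insufficiency*, reported as its own line, and state that biochemical suppression was not assessed.
2. Before enrolment, fix one numeric criterion for hypertension and one for hyperglycemia. Apply each to charted values in both arms, over the same hours from enrolment and regardless of the cause attributed.
3. Report each component separately by arm, together with the proportion of each arm that had at least one glucose measured. A cut-off cannot correct for children who were never tested. This proportion shows how far testing differed between the arms but does not remove the difference.

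The cost is protocol wording and some added chart abstraction, with no new test and no change to treatment. The downside is a narrower adverse-event claim, because adrenal suppression can no longer be presented as assessed.

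### Non-randomised arms are to be compared by unadjusted tests only, and steroid given before the first study dose is not on the list of data to collect

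*Combined protocol and SAP*

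**What the plan says.** Section 5a sets the design: "we will conduct a prospective, parallel-arm, non-randomized, open label, single-center, cohort study". On how children reach an arm it says only "Children consented to the interventional arm will receive intravenous (IV) DM", with the others enrolled to methylprednisolone (MP). The Study Summary gives a 2:1 ratio of standard care to intervention. No section says who is offered which arm, or on what basis.

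Section 7c names the comparative methods: "Comparative statistics will include Wilcoxon rank sum", Fisher's exact and Student's t tests. The Study Summary repeats this list. Neither document part mentions regression, stratification, matching, weighting or a sensitivity analysis.

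Section 7b lists the other data, starting with "anthropometrics, demographics, Pediatric Risk of Mortality-3 score Probability of Mortality, Pediatric Asthma Severity Score" and going on to asthma class, a second mortality risk score, comorbidities and 30-day readmission. Steroid received before the first study dose is not on the list. Section 5g does not exclude children who have had it.

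The protocol itself indicates that such exposure is to be expected. Section 5d states: "The use of DM has been adopted in the emergency room and inpatient acute care setting as standard care". Section 5e, on the half-life of DM, states that "2 days of dosing is the equivalent of 5 days of steroid exposure".

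**The concern.** Without randomisation, nothing in the design protects balance at baseline. With open-label treatment and no stated assignment rule, a reader cannot judge whether sicker children, or children already given DM in the emergency room, are more likely to enter one arm. If they are, and if those factors affect recovery, an unadjusted difference in LOS or albuterol duration mixes them with the effect of the study steroid.

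The two factors stand differently. A severity imbalance could be seen, because the scores are collected, but the plan does not correct for it. A prior-steroid imbalance could, as planned, be neither seen nor corrected.

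This matters because Section 4 powers the study for a comparison of LOS, and Section 9 says the study will supply "basic comparative data required to power and conduct a definitive, head-to-head trial of DM vs. MP".

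**Working it through.** **Step 1. Can the stated sample size be reproduced?** Section 4 gives 30 DM and 60 MP children, a 1-day change in LOS, power 0.8 and alpha 0.05. It gives no SD and does not say whether the test is one- or two-sided, so 90 cannot be reproduced from stated inputs. Assuming a two-sided test, it can be solved for the SD.

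- Normal approximation: SD = 1 / [√(1/30 + 1/60) × (1.960 + 0.842)] = 1 / (0.2236 × 2.802) = 1.60 days.
- Noncentral t, 88 degrees of freedom: SD = 1.58 days, a standardised difference of 1/1.58 = 0.633.
- Check: with SD 1.59 the normal formula returns 60 + 30 = 90.

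I use 1.58 below. The standard error (SE) of the LOS difference is 1.58 × 0.2236 = 0.353 day. A one-sided test would imply an SD of about 1.78 and an SE of 0.398.

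**Step 2. From imbalance to bias.** For a yes/no factor, bias = (difference between arms in the proportion with the factor) × (effect of the factor on LOS in days). The documents give neither term, so these inputs are assumed:

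- 20 points × 0.25 day = 0.05 day
- 20 points × 1 day = 0.20 day
- 40 points × 0.75 day = 0.30 day

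**Step 3. From bias to type I error.** With no true drug effect, the t statistic has noncentrality bias/SE. The two-sided rejection probability at a nominal 5% is:

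| Bias (days) | Bias/SE | Type I error |
|---|---|---|
| 0.05 | 0.14 | 5.2% |
| 0.20 | 0.57 | 8.7% |
| 0.30 | 0.85 | 13.4% |

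At the mild end, a 10-point imbalance in a factor worth 0.75 day gives 0.075 day and 5.5%, which is negligible. Using the Wilcoxon test instead of the t test does not remove the bias, since both compare the same unadjusted groups.

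**Step 4. What adjustment costs.** Take one severity term and two terms for prior steroid (DM, other, none).

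- Arms balanced, covariates unrelated to LOS: the SE rises from 0.353 to 0.359, and power for 1 day falls from 80% to 79%.
- Arms balanced, covariates predictive: assume severe illness is worth 1 day and prior DM 0.5 day, each present in half the children. They explain 0.25 × 1² + 0.25 × 0.5² = 0.3125 of the total variance 1.58² = 2.496. The residual SD is √(2.496 − 0.3125) = 1.48. The SE is 1.48 × 0.2236 × (0.359/0.353) = 0.336, and power is about 84%.
- Prior DM 70% in one arm and 30% in the other: arm and covariate are now correlated. The SE is about 0.396 and power about 70% if the covariates do not predict LOS. Power is about 77% if they do, with the effects above and total SD held at 1.58.

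**The case against.** The strongest reply is that nothing shows a problem. The documents report no imbalance, every input to the bias figures is assumed, and the 13.4% needs a large imbalance and a large effect together. Even 0.30 day is under a third of the 1-day target. If nearly every child receives DM in the emergency room, the prior-steroid bias is negligible. All of that stands, and it limits the point to a risk that the plan leaves uncontrolled.

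Two further replies stand in part. The word 'include' in 7c does not strictly rule out other methods; but no adjusted method is prespecified, and one chosen after seeing open-label data carries less weight. Prior steroid is probably recoverable, since the group's earlier study defined its cohorts by emergency-room DM; that makes the fix cheap but does not put the variable in the plan.

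Several stronger readings are tempting and should be resisted:

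- *Families choose the arm through consent.* The text does not say so. Consent is required of all participants, and the assignment rule is simply not stated.
- *The severity scores go unused.* Section 7c does not confine its descriptive and comparative statistics to the primary outcomes, so severity may well be shown by arm. Only adjustment is missing.
- *The earlier study settles whether emergency-room DM matters.* Section 4 reports "Our data revealed no differences, but many children were switched to MP during their PICU stay" and calls the analysis severely confounded for that reason. It neither supports nor excludes an effect.
- *A biased LOS difference will become the definitive trial's planning effect.* The documents say the data will help to power that trial, but not which estimate will be used. This softens the consequence. It does not remove the defect, because Section 4 states a powered LOS comparison for this study.

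**Conclusion.** The point holds as a gap in design and analysis that should be fixed. The arms are not randomised, the assignment rule is not stated, only unadjusted tests are planned, and one plausible confounder named by the protocol's own background is not on the data list. A difference between arms in severity or prior steroid would bias the LOS and albuterol contrasts to the extent that the factor affects those outcomes.

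The documents do not establish that such a difference exists, how large it is, or which arm it would favour. The illustrative type I error of 5.2% to 13.4% rests on a two-sided t test, a back-solved SD and assumed biases of 0.05 to 0.30 day. It shows how sensitive the planned test would be and is not an estimate of the bias in this trial.

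**What to change.** In 7b, add systemic corticosteroid received before the first study dose (agent, dose, time), taken from the chart, and report it by arm. State that the severity score used for adjustment is the one recorded before the first study dose.

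In 7c, prespecify one adjusted between-arm comparison for LOS and one for albuterol duration. Each should include prior systemic steroid and a single pre-dose severity score already in 7b, for example the Pediatric Asthma Severity Score. Report these beside the unadjusted tests.

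The cost is a few chart fields and a few degrees of freedom. Power for 1 day goes from 80% to about 79% if arms are balanced and the covariates do not predict LOS, or to about 84% if they predict it as assumed above. It falls to about 70–77% if prior DM is as unequal as 70% v 30%; in that case the unadjusted result would be hard to interpret if prior DM affects LOS. Adjustment deals only with recorded factors, so confounding by unrecorded ones remains and the report should say so. Eligibility and treatment are unchanged.
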